9.3 POPULATIONS FOR ANALYSES

All randomized participants will be included in the intent-to-treat (ITT) population. All randomized subjects who receive at least one dose of study product (CO vs. placebo) will be included in the safety analyses (*i.e.*.. modified ITT). For secondary and exploratory endpoints, subjects may also be analyzed according to the number of study drug doses completed.

9.4 STATISTICAL ANALYSES

9.4.1 GENERAL APPROACH

We will use the Mann-Whitney U or t-test, chi-square (χ^2) or Fisher's exact tests to analyze baseline demographics and clinical characteristics between the treatment groups. Distribution of numerical outcomes will be evaluated prior to any analysis. Numerical outcomes will be compared between treatment arms using the Mann-Whitney U or t-test and categorical outcomes compared using either χ^2 or Fisher's exact test.

9.4.2 ANALYSIS OF THE PRIMARY SAFETY ENDPOINT(S)

We hypothesize that iCO will be safe and well-tolerated and that our iCO dosing algorithm will be accurate

in achieving target COHb levels.

We will examine all AEs including pre-specified administration-related AEs by the type of event, as well as by body system class, and will report proportions and 95% CI. We will compare the occurrence of specific AEs in each arm by the χ^2 test, and the number of AEs per patient in each arm by the Wilcoxon-Mann-Whitney test.

COHb levels will be summarized descriptively reporting mean, standard deviation, median, minimum, and maximum at each time point, each day, by treatment arm. The mean difference between predicted and measured COHb levels with 95% confidence intervals will be presented for the iCO group. Repeated measures analysis of variance (ANOVA) will be used to assess the effects of treatment, time (over 3 days), and the interaction between time and treatment for 90-minute COHb levels. ANOVA will be repeated to assess the effects of treatment, time (over 3 days), entry criteria (ARDS/Sepsis vs. Non-ARDS/Sepsis Pneumonia vs. Non-ARDS/non-Sepsis Pneumonia), and two-way/three-way interactions of time, treatment and entry criteria. We will also compare the occurrence of COHb $\geq 10\%$ in each arm by the χ^2 test.

Accuracy of the CFK equation-based personalized iCO dosing algorithm to achieve target COHb levels will also be analyzed by Spearman correlation and Bland-Altman plots using measured vs. predicted COHb levels and modeled using linear or non-linear regression.

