8.7.6 ADVERSE EVENT REPORTING

All clinically important AEs as described in **Section 8.7.5**, will be recorded in the StudyTRAX database. For each AE, an email will be sent to the CCC, site PI, and blinded physician adjudicating AEs at each site. AEs will be summarized using System Organ Class and preferred terms. Tables will show by treatment group the number and percentage of participants experiencing an AE within a System Organ Class or within preferred term category by severity or by relationship to study product. For the calculations in these tables, a participant with multiple AEs within a category will be counted once under the maximum severity or the strongest recorded causal relationship to study product. Formal statistical testing comparing groups is not planned since interpretation of differences must rely heavily upon clinical judgment.

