9.2 SAMPLE SIZE DETERMINATION

As the primary endpoint of this Phase Ib trial is safety, this sample size of 36 (2:1 CO:placebo) was chosen based on a probability to estimate the mean difference between measured and predicted COHb levels in the CO group within 0.5% with 95% confidence to support the accuracy of the CFK equation.

Our preliminary data from our Phase Ia trial demonstrate that the CFK equation is highly accurate at predicting COHb levels following a 20 minute exposure to 200 ppm iCO ($r=0.916$, $R^2=0.9204$; $p<0.0001$). The mean difference between measured and predicted COHb levels was 0.1467 ± 0.2738 . Using a more conservative estimate of standard deviation (SD)=0.6, we will have >99% probability that 95% confidence intervals around the mean difference between measured and predicted COHb levels will be -0.353% to 0.647%. Our calculation includes an 8% dropout rate.

The goal of the safety evaluation for this study is to identify safety concerns associated with CO administration. The ability of the study to detect administration-related AEs or SAEs can be expressed by the true event rate above which at least one SAE would likely be observed and the true event rate below which no events would likely be observed. Specifically, for the CO arm of the study (n=24), there is a 90% probability of observing at least one AE if the true background rate of that AE is 10% and a 97% probability of observing at least one AE if the true background rate of that AE is 15%. For the placebo arm of the study (n=12), there is an 83% probability of observing at least one AE if the true background rate of that AE is 15% and a 91% probability of observing at least one AE if the true background rate of that AE is 20%. In our Phase Ia trial, there were no administration-related AEs and no SAEs related to study product or procedures.

Probabilities of observing one or more events between the groups are presented in **Table 6** below for a range of possible true AE rates. These calculations provide a more complete picture of the sensitivity of this study design to identify potential safety problems with CO.

Table 6. Probability of observing 1 or more events between the groups for different true AE rates

| CO group | | | Placebo Group | | |
|----------|--------------|-----------------------------|---------------|--------------|-----------------------------|
| n | True AE rate | Power to detect ≥ 1 AE | N | True AE rate | Power to detect ≥ 1 AE |

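### Section 8.7.6 rules out formal between-group testing of AEs while 9.4.2 and 9.4.5 prescribe it for the primary safety endpoint, and the chi-square test they name is unsuited to sparse 24 vs 12 tables

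*Combined protocol and SAP*

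**What the plan says.** Section 8.7.6 describes the AE tables: "AEs will be summarized using System Organ Class and preferred terms", by treatment group, with severity and relationship. It closes: "Formal statistical testing comparing groups is not planned since interpretation of differences must rely heavily upon clinical judgment".

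Section 9.4.2, on the primary safety endpoint, covers all AEs, including the administration-related ones, by type of event "as well as by body system class, and will report proportions and 95% CI". It continues: "We will compare the occurrence of specific AEs in each arm by the" chi-square test, "and the number of AEs per patient in each arm by the Wilcoxon-Mann-Whitney test". Later it adds: "We will also compare the occurrence of COHb" of 10% or more, again by chi-square. Section 9.4.5 repeats all of this.

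Section 9.4.1 gives the general rule: "Numerical outcomes will be compared between treatment arms using the Mann-Whitney U or t-test and categorical outcomes compared using either" chi-square or Fisher's exact test. It gives no criterion for choosing between them, and 9.4.2 and 9.4.5 name chi-square only.

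On how many events to expect, Section 9.2 reports: "In our Phase Ia trial, there were no administration-related AEs and no SAEs related to study product or procedures". Its Table 6 considers true AE rates from 1% to 20%.

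**The concern.** The incidence of pre-specified administration-related AEs and SAEs is the first primary endpoint. One section says differences between arms are a matter of clinical judgment without testing. Two others prescribe the tests. The plan cannot be followed as written, and whoever writes the final report must decide after the fact whether AE p-values appear.

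If they do appear, the test matters. With 2:1 allocation and few events, a small chance cluster in the 12 placebo subjects weighs far more than the same number of events among the 24 CO subjects. A nominally significant AE difference in favour of the study drug could then rest on two placebo events, while a real excess on CO would usually go unflagged.

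**Working it through.** **Do the sections cover the same events?** Section 8.7.6 tabulates AEs by arm, System Organ Class and preferred term. A preferred-term row, split by arm, is the occurrence of a specific AE in each arm, which is what 9.4.2 and 9.4.5 send to chi-square. The overlap is at event level, and no section says which text governs.

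**Inputs.** Arms of 24 and 12 (Sections 4.1 and 9.2); true rates of 1% to 20% (Table 6). Alpha, sidedness and continuity correction are not stated for the AE tests. I assume two-sided 0.05, the only alpha in the plan (9.4.3), and no correction.

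**The plan's own safety figure.** Table 6 gives the probability of at least one event, 1 − (1 − p)^n. At p = 0.10 it prints 0.90 for CO. With n = 24 the formula gives 0.920; with n = 22 (24 × 0.92 = 22.1, the 8% dropout in 9.2) it gives 0.902. All 14 cells reproduce with 22 and 11 subjects. The n label is a separate matter. Table 6 says nothing about the chi-square test, for which no power is stated.

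**Sparsity.** The expected placebo count is events × 12/36, so the conventional minimum of 5 needs 15 events among 36 subjects. P(15 or more) is 7 × 10⁻⁷ at a 10% rate and 0.25% at 20%. At a 1% rate, 0.99^36 = 70% of trials have no event in either arm and chi-square cannot be computed.

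**One table by hand.** Take 0/24 CO vs 2/12 placebo.
- Pearson: 36 × (0 × 10 − 24 × 2)² / (24 × 12 × 2 × 34) = 82,944 / 19,584 = 4.24, p = 0.040.
- Fisher: both events on placebo has probability C(12,2)/C(36,2) = 66/630 = 0.105. The other two splits are more probable, so this is the two-sided p.

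In the other direction, with no placebo events, Pearson needs 7/24 on CO for p < 0.05 (p = 0.037; Fisher 0.070), and Fisher needs 8/24.

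**Type I error.** I enumerated all 25 × 13 tables, weighted each by its binomial probability under a common rate, and summed those with p < 0.05. Favouring CO means a false signal of excess AEs on placebo.

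| Common rate | Pearson total | favouring CO | against CO | Fisher total | favouring CO | against CO |
|---|---|---|---|---|---|---|
| 1% | 0.49% | 0.49% | ~0 | 0.02% | 0.02% | ~0 |
| 5% | 3.55% | 3.54% | 0.007% | 0.66% | 0.66% | 0.001% |
| 10% | 3.70% | 3.49% | 0.21% | 1.61% | 1.56% | 0.05% |
| 15% | 3.84% | 2.98% | 0.86% | 2.15% | 1.86% | 0.29% |
| 20% | 4.69% | 3.12% | 1.56% | 2.47% | 1.77% | 0.70% |

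From 5% upward the Pearson error favouring CO exceeds a nominal 2.5% tail; Fisher's stays below 2%. At 5% the single table 0/24 vs 2/12 has probability 0.95^24 × 66 × 0.05² × 0.95^10 = 2.9% and supplies most of the 3.54%. Pearson and Fisher fall on different sides of 0.05 in 2.9%, 2.1% and 2.2% of trials per AE type at rates of 5%, 10% and 20%.

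With 22 vs 11 subjects the pattern is the same: Pearson total 0.4% to 4.2% over the Table 6 rates, and 0/22 vs 2/11 gives 0.039 against 0.104.

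**Power to flag harm (CO vs placebo rate).** 20% vs 0%: Pearson 18.9%, Fisher 8.9%. 20% vs 5%: 10.6% and 5.0%. 30% vs 5%: 38.4% and 26.2%.

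**The case against.** The best defence reads 8.7.6 as governing only its own summary tables and Section 9 as governing the analysis. It is right on one detail: in 9.4.2 the grouping by body system belongs to the descriptive sentence on proportions and CIs, and the test sentence concerns specific AEs only. It does not remove the conflict, because preferred-term tables and specific AEs are the same events, and the reason 8.7.6 gives for not testing applies equally to them.

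A second defence is that Fisher's test is already allowed in 9.4.1. That is so, and it makes the repair easy. But the specific sections name chi-square alone, and an analyst would follow the specific text.

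The defence of chi-square itself is stronger. Several readings are tempting that the documents and the figures do not support:
- *Chi-square inflates the false-positive rate.* At the Table 6 rates it does not; the total stays below 5%. The problem is where the error falls.
- *Fisher cures the imbalance.* It shrinks the error in both directions but is relatively no less lopsided: at a 10% rate, about 16 to 1 for Pearson and more than 30 to 1 for Fisher. The imbalance comes largely from 2:1 allocation with few events.
- *Fisher is the safer choice for patients.* It roughly halves the power to flag harm at a 20% CO rate. This is a reason to prefer intervals to any test.
- *A faulty p-value could decide whether the trial stops.* Section 9.4.6 lets the EC or DSMB halt enrollment at any time, and no section makes a p-value a stopping or safety criterion.
- *The unnamed CI method, the unstated continuity correction and the between-arm COHb comparison are defects in their own right.* The first two are missing detail, which a fuller SAP might supply (Section 6.1.4 refers to one for a conversion that Section 9 does not contain). The third is a matter of presentation.

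**Conclusion.** The point holds. Section 8.7.6 and Sections 9.4.2 and 9.4.5 give opposite instructions for the same events on the first primary endpoint. The test named in the latter two is unsuited to the expected tables: at a 5% rate its 3.5% error in favour of CO compares with 0.007% against, and two placebo events alone can produce p = 0.040.

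The consequence is modest. The choice between Pearson and Fisher changes the side of 0.05 in about 2% to 3% of trials per AE type at the 5%, 10% and 20% rates, and only the final safety report is affected. The figures rest on two-sided 0.05, no continuity correction, 24 and 12 dosed subjects, independent subjects and one AE type at a time. The contradiction in wording rests on none of these.

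**What to change.** Reconcile the three sections in one of two ways.

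1. Preferred: follow 8.7.6. Remove the AE tests from 9.4.2 and 9.4.5 and report per-arm AE proportions with exact (Clopper-Pearson) 95% CIs. For scale, 0/24 has an upper limit of 14.2% and 0/12 of 26.5%, which shows the reader how little zero events exclude.
2. If a comparison is kept: name Fisher's exact test, already permitted by 9.4.1, in place of chi-square in 9.4.2 and 9.4.5. Label it and the Wilcoxon-Mann-Whitney comparison descriptive, and amend the closing sentence of 8.7.6 to match. Keep the exact CIs.

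The cost is protocol and SAP wording only, with no new data. The downside of the second option is Fisher's lower power, so the text should say that a non-significant AE comparison is not evidence of safety. The change should be made before the unblinded final analysis.

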More recently, we completed a Phase I trial of low fixed-dose iCO in patients with sepsis-induced ARDS^{111,112}. Twelve participants were randomized to iCO or placebo air 2:1 in two cohorts. Four subjects each were administered iCO (100 ppm in Cohort 1 or 200 ppm in Cohort 2) or placebo for 90 minutes for up to 5 consecutive days. CO treatment was well tolerated and no participants exceeded a COHb level of 10%. There were no administration-associated AEs or study-related serious AEs (SAEs). Baseline COHb levels were not different across treatment groups. CO-treated participants had a significant increase in COHb ($3.48 \pm 0.7\%$ [Cohort 1]; $4.9 \pm 0.28\%$ [Cohort 2]) compared with placebo-treated subjects ($1.97 \pm 0.39\%$), which did not differ from baseline levels (Figure 2). The maximum COHb

(Figure 2). The maximum COHb

level in Cohort 1 was 4.4% and 6.87% in Cohort 2. The maximum change in COHb from baseline to 90 minutes (Δ 90 min COHb) was 2.5% in Cohort 1 and 4% in Cohort 2. There was no significant increase in COHb in placebo subjects.

Taken together, these findings demonstrate that experimental administration of several different concentrations of CO is well tolerated and that low dose iCO can be safely administered to subjects in a controlled research environment.

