In our recently completed Phase I fixed dose iCO trial, we also found an excellent correlation between measured and predicted COHb levels using the CFK equation¹¹². While the CFK equation is a well-validated model of CO uptake that accurately predicts the rise in COHb following CO exposure in humans with normal lung function⁹⁷⁻¹⁰³, it had not been previously used in ARDS patients with impaired gas exchange before. We found an excellent correlation in participants treated with 100 ppm iCO (Spearman $r= 0.8614$; $p<0.0001$), but an even stronger correlation in subjects treated with 200 ppm iCO (Spearman $r=0.916$; $p<0.0001$) (Figure 8A). Modeling the 200 ppm Cohort 2 data with linear regression revealed a slope of 1.112 (95% confidence interval [CI] [1.003, 1.22]), a y-intercept of -0.6632 (95% CI [-1.174, -0.1522]), and goodness-of-fit $R^2=0.9204$ ($p<0.0001$). Bland-Altman plots also demonstrated excellent agreement between measured and CFK equation-predicted COHb levels (Figure 8B) with a mean difference between measured and predicted COHb levels of 0.1467 ± 0.2738 in Cohort 2 (200 ppm).

The above predictions using the CFK equation were made using a MATLAB-generated computer program to estimate DLCO using the baseline and 20 minute COHb. The estimated DLCO was then input into the programmed CFK equation and used to predict the 60, 75, and 90 minute COHb levels. This program was validated by generating the previous published curves (Figure 1) that were derived from predicted values using the CFK equation¹⁰¹.

[figure not shown]

Figure 8. CFK equation accurately predicts COHb levels in ARDS patients.

CFK Equation For Precision-Based iCO Dosing

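### The predicted-minus-measured COHb interval has no stated time point, unit of analysis or within-patient term, and will be too narrow if repeated readings are pooled

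*Combined protocol and SAP*

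**What the plan says.** Accuracy of the CFK-based algorithm is the second primary endpoint. Section 3 describes it as a comparison of measured 90-minute COHb with the 6-8% target.

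Section 9.4.2 (repeated in 9.4.5) plans three kinds of analysis for COHb:

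- An interval for the bias of the prediction: "The mean difference between predicted and measured COHb levels with 95% confidence intervals will be presented for the iCO group".
- Agreement statistics: accuracy "will also be analyzed by Spearman correlation and Bland-Altman plots using measured vs. predicted COHb levels", followed by linear or non-linear regression.
- A within-patient analysis of a different quantity: "Repeated measures analysis of variance (ANOVA) will be used to assess the effects of treatment, time (over 3 days"), with its interaction with treatment, for 90-minute COHb levels. It is then repeated with entry criteria added.

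Sections 6.1.3 and 6.1.4 provide for treatment on up to 3 days, with COHb read at 20, 40, 60, 75, 90 and 180 minutes on each. Section 9.2 sizes the iCO arm to "estimate the mean difference between measured and predicted COHb levels in the CO group within 0.5% with 95% confidence" and counts subjects. It does not mention repeated readings.

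**The concern.** Readings from one patient are likely to be correlated. All predictions on a given day rest on one DLCO estimate from the baseline and 20-minute COHb (6.1.3, 6.1.5), so an error in that estimate moves the day's later predictions together. An interval that counts each reading as an independent observation overstates the information available.

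The bullets for the lung endpoints (9.4.3) and for 90-minute COHb levels name repeated-measures methods. The predicted-versus-measured analyses name none, so the choice is left to whoever runs them. The background section gives a reason not to assume that the gap will be filled well: the Phase Ia agreement figures look like pooled readings.

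At stake is how precisely the trial will say it knows the algorithm's bias, together with any p-value or interval attached to the correlation, regression or limits of agreement.

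**Working it through.** **1. The plan's own figure.** Inputs from 9.2: "The mean difference between measured and predicted COHb levels was 0.1467 ± 0.2738"; "Using a more conservative estimate of standard deviation (SD)=0.6"; margin 0.5; 8% dropout, so 24 iCO patients become 22.

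- Interval: 0.1467 ± 0.5 = -0.353 to 0.647, as stated.
- With one value per patient, the expected half-width is t(0.975, 21) × 0.6/√22 = 2.080 × 0.1279 = 0.266. At n = 24 it is 0.253.
- The half-width is at most 0.5 when the sample SD is at most 0.5 × √22/2.080 = 1.128. The probability of that is P(χ² on 21 df ≤ 21 × 1.128²/0.36 = 74.2), which exceeds 0.9999.

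The stated >99% is therefore reproduced with one value per patient.

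**2. What Phase Ia did.** From 2.2.9: "Modeling the 200 ppm Cohort 2 data with linear regression revealed a slope of 1.112", with 95% CI 1.003 to 1.22 and R² = 0.9204. From 2.2.5: "Four subjects each were administered iCO (100 ppm in Cohort 1 or 200 ppm in Cohort 2"), for up to 5 days.

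For ordinary least squares with one predictor:

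- SE = (1.22 - 1.003)/2 ÷ t(0.975, df), T = slope/SE, and df = T²(1 - R²)/R².
- At df = 37: SE = 0.1085/2.026 = 0.0535; T = 1.112/0.0535 = 20.77; T² × 0.0796/0.9204 = 37.3. The solution is df of about 37, or about 39 points.
- Four patients for at most 5 days give at most 20 patient-days. So 39 points need more than one reading per patient-day.
- A two-sided exact Spearman p-value from four independent values cannot be below 2/4! = 0.083. The documents report p<0.0001.

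Both checks indicate that repeated readings were treated as separate observations.

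**3. Size of the effect if this trial does the same.** With m readings per patient and common correlation ICC, the design effect is DEFF = 1 + (m - 1) × ICC. The pooled interval is too short by a factor √DEFF, and its actual coverage is 2Φ(1.96/√DEFF) - 1. The ICC is an assumption; the documents give none.

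- m = 3: the 90-minute reading on each of 3 days, matching the endpoint definition in section 3.
- m = 9: the 60, 75 and 90-minute readings on each of 3 days. These are the times predicted in Phase Ia (2.2.9).

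| m | ICC | DEFF | √DEFF | Coverage of nominal 95% CI |
|---|---|---|---|---|
| 3 | 0.2 | 1.4 | 1.18 | 90% |
| 3 | 0.4 | 1.8 | 1.34 | 86% |
| 3 | 0.6 | 2.2 | 1.48 | 81% |
| 9 | 0.2 | 2.6 | 1.61 | 78% |
| 9 | 0.4 | 4.2 | 2.05 | 66% |
| 9 | 0.6 | 5.8 | 2.41 | 58% |

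In half-widths (n = 22, SD 0.6), the pooled interval would be about ±0.147 for m = 3 and ±0.084 for m = 9. The correct half-width, 2.080 × 0.6 × √(DEFF/(22m)), is 0.182 to 0.228 for m = 3 and 0.143 to 0.214 for m = 9 over ICC 0.2 to 0.6. These ratios slightly exceed √DEFF because the t quantile has 21 df.

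**4. Limits.** At ICC = 0 there is no meaningful loss. At ICC = 1 the correct half-width is 0.266 for any m, the one-value-per-patient figure in step 1.

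**The case against.** The strongest reply is that the plan is silent, not wrong. Nothing in 9.4.2 says that readings will be pooled. The descriptive COHb summaries there are by time point and day, and 9.2 counts subjects. One value per patient would give a valid interval. This stands: a reader might infer from Phase Ia that the new intervals are bound to be far too narrow, but a completed study's analysis shows a risk, not a plan.

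The plan also does not ignore within-patient correlation throughout. The repeated measures ANOVA covers 90-minute levels, which is the quantity section 3 names for accuracy. That stands too, but the ANOVA does not yield the predicted-minus-measured interval for which the trial was sized.

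A reader might also count twelve readings per patient by adding the 40-minute draw and arrive at a larger effect. The documents describe predictions only at 60, 75 and 90 minutes, and section 8.5 gives safety monitoring as the purpose of the 40-minute and later draws. Holds, early stopping and extubation would reduce the count further. Nine is the most that the described predictions support.

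Finally, only the mean difference has a stated confidence interval, and regression wording leaves the error structure open. Pooling also hardly moves the Bland-Altman limits themselves: with m = 9 and ICC 0.6, the expected pooled variance falls by 8 × 0.6/197 = 2.4%. What pooling distorts is the precision attached to those limits. None of this answers the absence of a unit and time point for the one interval that is planned.

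**Conclusion.** The omission is real and concerns the quantity on which section 9.2 bases the sample size. Sections 9.4.2 and 9.4.5 need a time point, a unit of analysis and a within-patient method for predicted-versus-measured COHb. The Phase Ia figures make pooling a realistic outcome if the text stays as it is.

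The size is conditional on pooling and on an assumed ICC of 0.2 to 0.6: modest with three 90-minute values per patient (interval about 1.2 to 1.5 times too short), and larger with nine values (about 1.6 to 2.4 times). The calculation assumes complete data and one common correlation. Readings within a day may be more alike than readings on different days.

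A reader might infer that the trial is undersized. It is not: even in the worst case the half-width is about 0.27 against the 0.5 target, and sections 9.2 and 9.4 attach no success criterion or stopping rule to this interval. The exposure is in the reported precision.

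**What to change.** Amend 9.4.2 and 9.4.5 to state the following:

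- The primary mean predicted-minus-measured difference is taken at 90 minutes, with the patient as the unit.
- Its 95% CI comes from a mixed model with a patient random effect, plus day within patient if several readings per day are used. Alternatively, it comes from one averaged difference per patient with a one-sample t interval.
- Bland-Altman limits use the repeated-measures form.
- Any interval or p-value for the correlation or regression uses patient-clustered standard errors or a bootstrap that resamples patients.

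The cost is SAP wording, a little more analysis work and wider reported intervals. No additional patients or measurements are needed, and the precision target is still met. This is a cheap improvement.
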